6.2.1 Screening and run-in period(s)

Visit 1/Day -1 – Screening and dispensing visit

Informed consent must be obtained prior to any trial related procedures taking place.

Tests for which results are not already available as part of the patient's standard of care, may be ordered after the patient signs informed consent.

Prior to determining eligibility the investigator should: 1) review all information obtained at this visit, 2) review the inclusion/exclusion criteria and 3) confirm that the patient has discontinued all prohibited therapy or medications (see Sections 4.2.2 and 4.2.2.1) and an adequate washout period has passed.

Table 6.2.1: 1 Visit 1 /Day -1 – Screening and dispensing visit

	The following must be performed and information recorded in the patient's chart	What to include in eCRF
Informed Consent	Written informed consent must be obtained prior to any trial related procedures taking place.	Date of informed consent
Demographics	Obtain the following demographic data: sex, birth date, race, smoking and alcohol history	Sex, birth date, race, ethnicity, and smoking history

Doc. No.: U13-1326-02

08 Feb 2021

Page 50 of 95

Trial Protocol

	The following must be performed and information recorded in the patient's chart	What to include in eCRF
Medical history	Oncological and relevant non-oncological	History of NSCLC:
	history including details of previous treatment for NSCLC (including pathology)	Oncological and relevant non-oncological history including details of any previous treatment for NSCLC
		• The date of first histological diagnosis, the primary tumour site, the number and location of metastatic sites (bone, brain, liver, pleural effusion, other)
		Tumour assessment/stage at the time of diagnosis according to the TNM-classification
		• Previous surgeries for NSCLC
		• Previously administered chemo-, immuno-, hormone therapy will be reported including start and end dates, the treatment regimen with the number of courses (chemo-immunotherapy), the best response obtained (complete response, partial response, stable disease, progressive disease, unknown), and progression date.
		Previous radiotherapy - the total radiation dose and radiation field will be recorded
Inclusion and Exclusion criteria	Assessment of eligibility according to inclusion and exclusion criteria should be performed.	Verify that the patient has met all the inclusion and exclusion criteria.

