7.7 EXTENT OF EXPOSURE

Total treatment time (days) will be calculated for each patient; total treatment time will include any dose interruptions or off-drug periods.

The definition of exposure is:

Treatment stop date – treatment start date + 1

In case of death (due to any cause), the treatment stop date will be imputed as the earlier of (date of last administration of afatinib, date of death) + 1 day.

Standard descriptive summaries of these data will be provided for the treated set of patients.

Total treatment time (days) will be summarized by afatinib dose level (40 mg, 30 mg, 20 mg and total), and by number of therapy lines at the 40 mg dose. The number of therapy lines for afatinib will be derived as: the number of all previous therapy lines + 1. The number of all previous therapy lines that the patient received prior to the start of treatment includes number of lines of all of the following:

- Systemic chemotherapies: count the number of previous chemotherapies with “therapy mode” as “advanced/palliative” on the previous chemotherapies eCRF page. If “therapy mode” is “neo-adjuvant” or “adjuvant” and taken within 1 year prior to study enrolment, then count them as a separate “line of therapy”.
- Other anti-cancer therapies: count the number of anti-cancer therapies with “therapy mode” as “advanced/palliative” on the other anti-cancer therapies eCRF page. If “therapy mode” is “neo-adjuvant” or “adjuvant” and taken within 1 year prior to study enrolment, then count them as a separate “line of therapy”. If there is a therapy with the same name and same start and end dates as a therapy present in previous systemic chemotherapies eCRF page, then ignore this as it has already been counted earlier.

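### The SAP 7.7 line count can score one concurrent regimen as two prior lines, placing some pre-treated patients a line too late in the exposure-by-line summary

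*SAP*

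**What the plan says.** SAP 7.7 (Extent of exposure) states that "The number of therapy lines for afatinib will be derived as: the number of all previous therapy lines + 1". Previous lines come from two sources, which are summed.

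- **Systemic chemotherapies page:** "count the number of previous chemotherapies with" a therapy mode of advanced/palliative.
- **Other anti-cancer therapies page:** "count the number of anti-cancer therapies with" the same mode.

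On both pages, a neo-adjuvant or adjuvant entry also contributes if it was given recently enough: "and taken within 1 year prior to study enrolment, then count them as a separate" line.

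The only exclusion applies to the second page: "If there is a therapy with the same name and same start and end dates as a therapy present" on the chemotherapy page, the entry is ignored because it has already been counted. Name, start date and end date must all agree. The section has no rule for therapies given at the same time under different names.

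The resulting number is used in the same section to break down treatment time at the 40 mg dose. Protocol 6.2.1 (Table 6.2.1: 1) sets out what is recorded on prior chemo-, immuno- and hormone therapy: it "will be reported including start and end dates, the treatment regimen with the number of courses", together with best response and progression date.

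**The concern.** A line of therapy is normally a regimen: drugs given together form one line. The SAP rule counts rows. When a regimen combines chemotherapy with an agent that belongs on the other page, the two rows have different names and the duplicate check cannot link them. The patient then appears to have had two previous lines.

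The duplicate check shows that the authors expected the same treatment to turn up on both pages, but it catches exact copies only. The same drug on both pages with end dates one day apart passes as two lines.

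At stake is the labelling of rows in the exposure-by-line summary. The third-line row would contain patients with one prior regimen, and the second-line row would lose them. Concurrent agents can only add to the count, so the error does not average out and a larger sample does not reduce it.

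**Working it through.** The SAP states no figure for this quantity, so there is none to reproduce. The check applies the rule as written to constructed histories and compares it with a count by regimen.

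**Inputs, all from SAP 7.7**

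- C = qualifying entries on the chemotherapy page.
- O = qualifying entries on the other anti-cancer page that do not match a chemotherapy entry on name, start date and end date together.
- SAP line for afatinib = C + O + 1.

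**Comparator.** R = number of groups left after merging qualifying entries on both pages whose dates overlap. Regimen-based line = R + 1.

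| Constructed history | SAP: C + O + 1 | By regimen: R + 1 |
|---|---|---|
| No prior therapy | 0 + 0 + 1 = 1 | 0 + 1 = 1 |
| One chemotherapy regimen only | 1 + 0 + 1 = 2 | 1 + 1 = 2 |
| Same regimen on both pages, identical dates | 1 + 0 + 1 = 2 | 1 + 1 = 2 |
| Chemotherapy plus a differently named agent, same dates | 1 + 1 + 1 = **3** | 1 + 1 = **2** |
| As above, agent continued longer | 1 + 1 + 1 = **3** | 1 + 1 = **2** |
| Same regimen on both pages, end date one day apart | 1 + 1 + 1 = **3** | 1 + 1 = **2** |
| Two chemotherapy lines, each with a concurrent agent | 2 + 2 + 1 = **5** | 2 + 1 = **3** |
| Chemotherapy doublet entered as two rows on one page | 2 + 0 + 1 = **3** | 1 + 1 = **2** |
| Second agent started after chemotherapy ended | 1 + 1 + 1 = 3 | 2 + 1 = 3 |

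**Which patients can move.** With no qualifying entry, both counts give 1. With at least one, both give 2 or more. No patient crosses between line 1 and line 2; any shift is from line 2 upward.

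**How many move.** The documents do not say. Let p be the share of patients with one prior regimen who have a concurrent agent as its own row on the second page. Then 100 × p per 100 such patients move from second to third line. For assumed p of 0%, 5%, 10%, 20% and 30%, that is 0, 5, 10, 20 and 30 per 100. These values of p are illustrations without a source, and the result simply repeats them.

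**The case against.** The strongest reply is that the fault depends on an eCRF that is not in the documents. Protocol 6.2.1 describes prior treatment by regimen, with courses, a best response and a progression date. SAP 7.7 itself describes the total as a number of lines. If each combination was entered once as a regimen, the rule gives the right answer. The second page may also be thinly used: prior EGFR-TKI treatment is excluded (Protocol 3.3.3), and radiotherapy and surgery do not enter the count. This stands as a limit on size. It does not rescue the rule, whose result should not depend on how a site split its entries.

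The consequence is also small. The one visible use is a descriptive exposure table. The primary endpoint is the number of patients with adverse events (SAP 5.1), the adverse-event tables in SAP 7.8.1 are not specified by line, and Protocol 7.2 plans no hypothesis test. This stands.

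A simple merge of overlapping dates has its own faults. It could join two true lines whose dates overlap slightly, it leaves open whether maintenance started after chemotherapy is a new line, and it must also cover (neo)adjuvant entries. This stands too, and the fix has to deal with it.

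A reader might infer that the treatment-naive versus pre-treated contrast in the trial's title is distorted. It is not, because no patient can cross from line 1 to line 2 through this fault. A reader might also infer that efficacy or subgroup results by line are affected. SAP 6.4 and the further-endpoint sections are redacted, so that can be neither confirmed nor excluded.

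**Conclusion.** The point holds within narrow limits. As written, SAP 7.7 gives the wrong line number when a concurrent agent has its own row on the other anti-cancer page, or when a duplicate differs by as little as a day. The size is one line per such regimen: 3 instead of 2 for one regimen, 5 instead of 3 for two.

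The effect is confined to second versus third or later line among pre-treated patients, in the summary of treatment time by line at 40 mg. The number of patients cannot be derived from the documents and may be zero, so a claim that a material share is misclassified would not be supported.

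The conclusion rests on two assumptions: that a line means a regimen of drugs given together, and that at least some combinations were entered as separate rows. It is worth correcting because a stated rule yields a wrong label and the repair is cheap. It does not threaten the trial's main result.

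**What to change.** Amend SAP 7.7 so that, before 1 is added:

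1. All qualifying entries across both pages (advanced/palliative, and neo-adjuvant or adjuvant within one year of enrolment) that were given concurrently as one regimen count as one line. Identify them by overlapping dates with no recorded progression between their start dates.
2. One convention is stated for a maintenance agent started after chemotherapy ends without progression: either it continues the line or it opens a new one. Date overlap does not settle this.
3. Short overlaps and overlaps that rest on partial dates go to medical review before database lock, so that two true lines are not merged.

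No new data are needed, since Protocol 6.2.1 already asks for start, end and progression dates of prior therapy. SAP 7.8.1 already uses comparable date logic to collapse repeated adverse-event records into episodes. The cost is a wording change, a small programming step and review of a few cases. The remaining downside is some judgement in those cases, which review before lock keeps documented.

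A quick first step is to list the pre-treated patients whose line number differs between the two counts. If there are none, the wording change has no effect on the table.

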7.8 SAFETY ANALYSIS

All safety analyses will be performed on the treated set.

7.8.1 Adverse events

The intensity of AEs were classified and recorded according to the Common Terminology Criteria for Adverse Events (CTCAE) version 3.0 in the eCRF.

Unless otherwise specified, the analyses of AEs will be descriptive in nature. All analyses of AEs will be based on the number of patients with AEs and NOT on the number of AEs.

Furthermore, for analysis of AE attributes such as duration, severity, etc. multiple AE occurrence data on the CRF, will be collapsed into AE episodes provided that all of the following apply:

- The same MedDRA lowest level term was reported for the occurrences
- The occurrences were time-overlapping or time-adjacent (time-adjacency of 2 occurrences is given if the second occurrence started on the same day or on the day after the end of the first occurrence)
- Treatment did not change between the onset of the occurrences OR treatment changed between the onset of the occurrences, but no deterioration was observed for the later occurrence

For further details on summarization of AE data, please refer to the guideline ‘Handling and summarization of AE data for clinical trial reports and integrated summaries’ [\(2\)](#) [001-MCG-156]

The analysis of AEs will be based on the concept of treatment emergent AEs. That means that all AEs occurring between first study treatment intake until 28 days after last study treatment intake will be assigned to be treatment-emergent. All AEs occurring outside of this period will be handled according to the treatment definition period definitions detailed in [section 6.1\(Treatment\)](#) and will only be listed unless stated otherwise.

An overall summary of AEs will be presented. This summary will exclude the rows ‘Severe AEs’, ‘Significant AEs’ and ‘Other significant AEs’ but will include additional rows for ‘AEs leading to dose reduction’ and ‘AEs by highest Common Terminology Criteria for Adverse Events (CTCAE)’ grade.

The frequency of patients with AEs will be summarised by highest CTCAE grade (grades 3, 4, 5 and all grades including grade 1 and 2), treatment, primary system organ class (SOC) and preferred term (PT) for each of the following AE tables:

- All AEs collected
- Drug related AEs
- AEs leading to dose reduction
- AEs leading to treatment discontinuation
- Drug related AEs leading to treatment discontinuation
- Serious AEs
- Drug related serious AEs
- AEs leading to death

All tables will be sorted by SOC according to the standard sort order specified by the European Medicines Agency (EMA); PTs will be sorted by frequency (within SOC).

The above tables except for AEs leading to death will be repeated for the project-defined grouping of AE terms (rash, stomatitis, ocular effects, lip effects, nail effects and fatigue). Details of the project-defined groupings are defined in the technical TSAP. In these tables the grouped AEs will replace the original PTs for all AEs that are included within the grouped term. The grouped AE categories will then be tabulated along with all remaining MedDRA PTs, sorted by descending frequency. A reference table presenting all of the project defined groupings and MedDRA PTs within each grouping will also be produced.

Additional AE tables will be produced for AEs of special interest (diarrhoea, and the project defined groupings of rash and renal insufficiency), providing further details on highest CTCAE grade, action taken with study drug and time to first onset of AE.

Number of patients with AEs with an incidence greater than 5% will be summarised by treatment, primary SOC and PT.

7.8.2 Laboratory data

Only the date of samples is collected; laboratory data are not collected. Laboratory values that are considered clinically relevant will be recorded as baseline conditions or AEs as appropriate.

7.8.3 Vital signs and physical examination

Only descriptive statistics are planned for this section of the report. A summary of the absolute values and the changes from baseline will be presented in 4-week periods and at the EoT visit for the following parameters: systolic blood pressure, diastolic blood pressure, pulse rate, temperature, and body weight.

Other than at baseline, repeat, adhoc or unscheduled data will not be included in the summary tables.

A listing for pregnancy test results of patients with child bearing potential will be provided.

A listing for LVEF results of patients will also be provided. Patients with a significant LVEF event will be flagged in the listing; a significant event is defined as a decrease of $\geq 20\%$ from baseline that is also below the lower limit of normal for the particular site (50% will be used if the lower limit of normal is missing).

7.8.4 ECG

[figure not shown]
Only the date of the tracing is collected. Abnormalities will be recorded as baseline conditions or AEs as appropriate.

7.8.5 Others

Not applicable.

10. HISTORY TABLE

Table 10: 1 History table

Version	Date (DD-Mmm-YY)	Author	Sections changed	Brief description of change
Final	24-Apr-2017	[REDACTED]	None	This is the final TSAP without any modification
